3.1 General methods

All summaries for Group A and B will be done separately. The same presentations will be made for both groups, but for Group A, only descriptive statistics will be used and the presentations will not be done by treatment group since all subjects in group A received treatment at baseline.

All statistical analyses, including summary tables and data listings, will be performed using the SAS® system (version 9).

All efficacy, safety and baseline characteristics variables will be presented using descriptive statistics and in subject data listings. Continuous data will be summarized by descriptive statistics n (number of observations), mean, standard deviation, median, minimum and maximum value, while categorical data will be presented by number and percentage. Graphs might be used as appropriate.

CCI

Further details of efficacy analyses can be found in Section 3.3 and definition of endpoints in Section 1.4.

Any change made to the finalized statistical analysis plan (SAP) will be documented in the Clinical Study Report (CSR).

 GALDERMA	Title Statistical Analysis Plan 43CH1507	Doc id MA-32268
--	---	----------------------------------

3.2 Study subjects

3.2.1 Subject disposition

The number of subjects in each study population (i.e. FAS, PP and Safety) will be summarized by site and in total.

The disposition of subjects (including reasons for screening failures and withdrawals) will be presented by treatment group and in total. This presentation will also be done by site.

The number of completed and withdrawn subjects will also be presented by visit.

3.2.2 Protocol deviations

All withdrawn subjects will be listed individually, including at least subject number, date and reason for withdrawal, and last visit performed. Subjects with CSP deviations disqualifying them from PP will be listed individually, including subject number and observed deviation.

For this study, the protocol deviations that will exclude subjects from PP are identified (but not limited to) in Table 3-1 below.

Table 3-1. Protocol deviations.

Deviation	
GENERAL	
	Visit out-of-window
	* Follow-up at 6 months after last treatment performed earlier than 1 week before the scheduled visit or later than 2 weeks after the visit in Treatment Group
	* Follow-up at 6 months after randomization performed earlier than 1 week before the scheduled visit or later than 2 weeks after the visit in Control Group
EFFICACY	
	MMVS assessed by blinded evaluator
	* Not done for both sides of the face at 6 months after last treatment in Treatment Group, or at 6 months after randomization in Control Group
	* Pre-treatment MMVS not available for both sides of the face
	* More than 1 grade difference in baseline MMVS score between the two sides of the face
OTHER	
	Inclusion/exclusion criteria
	* Any key inclusion criteria not met
	* Any key exclusion criteria met

Deviations from the SAP will be documented in the CSR.

	Title Statistical Analysis Plan 43CH1507	Doc id MA-32268
--	---	----------------------------------

2017-04-21 09:20

Effective date:

Effective

Version: 1.0

3.2.3 Demographic characteristics

Subject demographic and baseline characteristics data will be summarized for the FAS population by treatment group and in total.

3.2.4 Medical history and concomitant medication/procedures

All summaries will be done by treatment group based on the FAS population. Concomitant medications will be coded using the World Health Organization (WHO) Drug Dictionary. Medical History will be coded according to MedDRA.

The number and percentage of subjects reporting medical history, and the number of conditions will be summarized by system organ class (SOC), in total and for ongoing conditions. Previous facial procedures, fillers or implants as collected in the medical history, will be summarized by procedure and treatment group.

The number and percentage of subjects reporting concomitant medications will be summarized. In addition, the number and percentage of subjects reporting concomitant medication, and the number of drugs (total number and the number of drugs ongoing at study end), will be summarized by reason. The same summaries will be done for concomitant procedures/treatments. Also, for concomitant medication, the number and percentage of subjects and the number of drugs, will be summarized by ATC code. Concomitant medications that started due to an AE will be summarized separately.

3.2.5 Post-treatment examinations

BMI will be summarized for the FAS population, by visit and group, using descriptive statistics. A summary of urine pregnancy test results by visit and group will also be provided.

3.3 Efficacy analysis

3.3.1 Datasets analyzed

All efficacy variables will be analyzed using the FAS population. The primary analysis will be repeated using the PP population. If it is deemed necessary, other analyses will be repeated using the PP population.

3.3.2 Handling of missing data

Number of missing values will be summarized and reported as appropriate. The baseline observation carried forward (BOCF) method will be used as the primary imputation method to handle missing data on MMVS up to the Month 6 visit in the FAS analysis set. This strategy is a conservative approach as it treats subjects with missing data as non-responders. Impact of missing data on the primary analysis for Month 6 endpoint will be evaluated by performing sensitivity

	Title Statistical Analysis Plan 43CH1507	Doc id MA-32268
--	---	----------------------------------

Effective date: 2017-04-21 09:20

Effective

Version: 1.0

analysis based on the PP population. In addition, missing data for the primary analysis will also be handled using the multiple imputation (MI) method.

All other endpoints will be analyzed on available data, i.e. no imputations will be done.

If the baseline value is missing, the screening value will be used instead.

Use of MI

The imputation using MI will assume a Missing Completely at Random (MAR) mechanism. The MI procedure of the SAS® system will be used to generate five sets of data with missing values imputed from observed data. It is expected that the pattern of missing data will be monotonic, with slight deviations being corrected by the Markov Chain Monte Carlo (MCMC) method of the MI procedure. Linear regression will be employed to model the missing MMVS score, with the following covariates included in the imputation model: treatment and non-missing data from earlier time points (baseline CCI [REDACTED]). The imputed datasets will be analyzed using the methodology described for the primary analysis of responder rates at Month 6. The results from the analysis of the multiple imputed datasets will be presented as appropriate. The seed number to be used will be 431507 (the clinical trial number of this study, with the letters removed).

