4.7 Schedule of events

Table 1. Schedule of Events for Group A and Treatment Group

	Group A and Treatment Group					
	Screening ^a	Baseline ^a / Initial treatment	Follow-up / Optional Touch-up	Follow-up ^b	Follow-up	Final visit / Early termination
	D-21 to D1	D1	4W(±3d) after randomization	4W(±3d) after touch-up	3M(±1w), 6M(±1w) and 9M (±2w) after last treatment	12M (±2w) after last treatment
Informed consent	X					
Height, Demography	X					
Weight	X	X	X	X	X	X
Medical history & concurrent diseases	X	X				
Concomitant medication/procedures	X	X	X	X	X	X
Vital signs		X ^c				
Laboratory tests	X		X		X ^c	X ^f
ECG	X					
Pregnancy test		X ^c	X ^c			X
Inclusion and Exclusion criteria	X	X				
Randomization		X				
Treatment		X	X			
MMVS (Blinded Evaluator)	X	X ^c			X	X
CCI						
Photography		X ^c	X ^{c, d}	X	X	X

Device deficiencies		X	X			
Assessment of AE	X	X	X	X	X	X
Study termination						X

a) Screening visit and baseline visit can be combined to one visit if feasible.

b) Only for subject receive touch-up treatment.

c) Prior to treatment, if treat performed.

CCI

e) Only performed at 6M.

f) Only performed at early termination if termination occurs before 6 months visit after last treatment

Table 2. Schedule of Events for Control Group

Activity	Control Group									
	Screening ^a	Baseline ^a	Follow-up	Follow-up	Follow-up /Treatment	Follow-up /Optional Touch-up	Follow-up ^b	Follow-up	Final visit / Early termination	
	D-21 to 1	D1	4W(±3d) after randomization	3M (±1w) after randomization	6M(±1w) after randomization	4W(±3d) after 6M treatment	4W(±3d) after touch-up	3M (±1w) after last treatment	6M (±1w) after last treatment	
Informed consent	X									
Height, Demography	X									
Weight	X	X	X	X	X	X	X	X	X	
Medical history & concurrent diseases	X	X								
Concomitant medication/procedures	X	X	X	X	X	X	X	X	X	

Vital signs		X			X ^c					
Laboratory tests	X				X ^c	X				X
ECG	X									
Pregnancy test		X			X ^c	X ^c				X
Inclusion and Exclusion criteria	X	X								
Randomization		X								
Treatment					X	X				
MMVS (Blinded Evaluator)	X	X		X	X ^c			X		X
CCI										
Photography		X	X ^d	X	X ^c	X ^c	X	X		X
CCI										
Device deficiencies					X	X				
Assessment of AE	X	X	X	X	X	X	X	X		X
Study termination										X

a) Screening visit and baseline visit can be combined to one visit if feasible.

b) Only for subject receive touch-up treatment.

c) Prior to treatment, if treat performed.

CCI

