1.4 Efficacy endpoints

1.4.1 Primary efficacy endpoint

Responder rate based on the MMVS as assessed by the blinded evaluator at 6 months after last treatment for the Treatment group, and at 6 months after randomization for the Control group.

A responder is defined as a subject who achieves a score of at least 1 grade improvement from baseline to 6 months on both sides of the face.

Effective date: 2017-04-21 09:20

Effective

Version: 1.0

 GALDERMA	<small>Title</small> Statistical Analysis Plan 43CH1507	<small>Doc id</small> MA-32268
CCI		

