 GALDERMA	Title Statistical Analysis Plan 43CH1507	Doc id MA-32268
---	---	--------------------

Table A 16. MMVS responder rate by treatment and side of the face at Month 6, Blinded Evaluator (FAS)

Assessment/Time Point	Treatment Group	# of Subjects in FAS	# of Responders	Proportion of Responders	95% Confidence Interval	P-Value
Right and Left Midface Combined at Month 6	Perlane-Lido	Xx	Xx	X.XX	X.XX, X.XX	
	Control	Xx	Xx	X.XX	X.XX, X.XX	
	Difference	-	-	X.XX	X.XX, X.XX	X.XX
Right Midface at Month 6	Perlane-Lido	Xx	Xx	X.XX	X.XX, X.XX	
	Control	Xx	Xx	X.XX	X.XX, X.XX	
	Difference	-	-	X.XX	X.XX, X.XX	X.XX
Left Midface at Month 6	Perlane-Lido	Xx	Xx	X.XX	X.XX, X.XX	
	Control	Xx	Xx	X.XX	X.XX, X.XX	
	Difference	-	-	X.XX	X.XX, X.XX	X.XX

Note: Subjects with a missing MMVS have their values imputed using BOCF up to Month 6.

Note: Responder is defined as a subject with an improvement of at least one grade on the MMVS from baseline.

Note: Responder rate is calculated as the number of Responders at the visit of interest divided by the number of subjects in the FAS population for the specific treatment group.

Note: P-values for the difference in proportions are based on the Fisher's Exact test.

Note: 95% Confidence Intervals are two-sided confidence intervals calculated using the exact interval.

Table A 17. MMVS responder rate by treatment and side of the face at Month 6, Blinded Evaluator (PP)

As Table A 16 (only Left and Right Side Combined)

Note: No imputation is used for PP analysis. Only subjects with complete data are included.

Note: Responder is defined as a subject with an improvement of at least one grade on the MMVS from baseline.

Note: Responder rate is calculated as the number of Responders at the visit of interest divided by the number of subjects in the PP population for the specific treatment group.

CCI

 GALDERMA	Title Statistical Analysis Plan 43CH1507	Doc id MA-32268
--	---	----------------------------------

Table A 18. Sensitivity analysis for the MMVS responder rate by treatment and side of the face at Month 6, Blinded Evaluator (FAS)

As Table A 16 (only Left and Right Side Combined)

Note: Missing MMVS values are handled using multiple imputation methods.

Note: Responder is defined as a subject with an improvement of at least one grade on the MMVS from baseline.

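### SAP 3.3.2 imputes the 4-grade MMVS by linear regression, and no visible rule turns the imputed values into grades or links the two sides, so the multiple-imputation check on BOCF is under-specified (minor)

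*SAP*

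**What the plan says.** SAP 3.3.2 makes BOCF the primary method for missing MMVS up to Month 6 and justifies it thus: "This strategy is a conservative approach as it treats subjects with missing data as non-responders". Two checks follow: a per-protocol analysis, and multiple imputation with five imputed datasets and a fixed seed.

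For the imputation, the SAP states: "Linear regression will be employed to model the missing MMVS score, with the following covariates included in the imputation model". The visible covariates are treatment and earlier data starting with baseline; the rest of the list is blacked out. Then: "The imputed datasets will be analyzed using the methodology described for the primary analysis of responder rates at Month 6".

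SAP 1.3.1 defines MMVS as a 4-grade scale rated separately on the right and left. SAP 1.4.1 requires "at least 1 grade improvement from baseline to 6 months on both sides of the face".

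In SAP Appendix A, Table A 18 reports this analysis. Its layout is given as "As Table A 16 (only Left and Right Side Combined", and its note says only: "Missing MMVS values are handled using multiple imputation methods". Table A 16, whose layout it follows, uses Fisher's exact test, which needs a yes/no status for every subject. For the per-protocol analysis, the note to Table A 17 says: "No imputation is used for PP analysis. Only subjects with complete data are included".

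**The concern.** A linear-regression draw for a missing score is a value such as 2.1, while the endpoint is a cut on whole grades applied to both sides. Two choices decide who becomes a responder: how the value is converted to a grade, and whether the left side is drawn with knowledge of the right. No visible sentence in SAP 3.3.2 or 3.3.3, or in the notes to Tables A 16 to A 19, makes either choice, although the SAP fixes even the random seed.

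The choices are not neutral. Where the typical true gain is exactly 1 grade, many unrounded draws fall just short of the cut on a given side, and requiring both sides compounds the loss. Drawing the sides independently compounds it further.

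Multiple imputation is the one planned check that replaces BOCF while keeping every FAS subject. If it also turns most missing treated subjects into non-responders, its agreement with BOCF says little about how far BOCF lowers the difference.

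**Working it through.** The plan states no figure on this point to reproduce. The sample-size text is redacted, and the documents give neither missing rates nor expected grade distributions.

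**Inputs**
- Allocation: 111 treated and 37 control (Protocol Synopsis); 148 × 3/4 = 111 and 148 / 4 = 37.
- True response pT = 88%, pC = 17% (assumed). For scale, the earlier US study in Protocol 2.4.2 had 88.7% and 16.0% at Month 2.
- Grade mix (assumed): baseline 2/3/4 with probability .35/.50/.15. Improvement 0/1/2 with .10/.65/.25 if treated; −1/0/1 with .04/.78/.18 if control. The second side's improvement differs by one grade in 6%.
- Missing at random within arm, at assumed rates mT and mC.
- Imputation: Bayesian linear regression on treatment and both baseline sides, five imputations. The left side is drawn with (joint) or without (separate) the imputed right side.

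**Step 1. Share of missing subjects imputed as responders (qT / qC), against a true 88% / 17%**
- Unrounded, joint: 47% / 4%
- Unrounded, separate: 30% / 0.4%
- Rounded and limited to 1–4, joint: about 82% / 20%
- Rounded and limited to 1–4, separate: 74% / 7%
- BOCF: 0% / 0%

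**Step 2. Bias in the treatment difference**

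bias = mT(qT − pT) − mC(qC − pC)

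Unrounded joint at 10/10: 0.10(47 − 88) − 0.10(4 − 17) = −4.1 + 1.3 = −2.8 points. BOCF at 10/10: −8.8 + 1.7 = −7.1.

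The table gives the formula result in points, with the simulated value in brackets. There were 2,000 trials per scenario, with Monte Carlo error about 0.1. Ranges, and the separate-and-rounded values, also draw on smaller runs of 600 to 800 trials.

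| Missing % treated/control | Unrounded joint | Unrounded separate | Rounded joint | Rounded separate | BOCF | Logistic |
|---|---|---|---|---|---|---|
| 10/10 | −2.8 (−2.7) | −4.1 (−4.1) | −0.9 (−0.9) | −0.4 (−0.3 to −0.5) | −7.1 (−7.1) | (−0.3) |
| 20/20 | −5.6 (−5.3) | −8.3 (−8.0) | −1.8 (−1.6 to −1.9) | −0.8 (−0.9 to −1.0) | −14.2 (−14.0) | (−0.5) |
| 5/20 | +0.6 (+0.7) | +0.4 (+0.5) | −0.9 (−0.9) | +1.3 (+1.4 to +1.5) | −1.0 (−0.9) | (−0.5) |
| 2/20 | +1.8 (+2.0) | +2.2 (+2.3) | −0.7 (−0.6) | +1.7 (+1.7 to +1.9) | +1.6 (+1.7) | (−0.4) |

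The logistic column imputes both-sides responder status from treatment and mean baseline MMVS.

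**Step 3. Unrounded bias as a share of the BOCF error**
- 10/10: 2.7/7.1 = 38% and 4.1/7.1 = 58%.
- 20/20: 5.3/14.0 = 38% and 8.0/14.0 = 57%.

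**Step 4. Why rounded and separate looks good at equal missingness**

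At 20/20 the treated error is 0.20(74 − 88) = −2.8 and the control error is 0.20(7 − 17) = −2.0. The difference is −2.8 + 2.0 = −0.8. Both arms are wrong and the errors offset. At 2/20 the treated error shrinks to 0.02 × (−14) = −0.3 while the control error stays at −2.0, so the net is +1.7.

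**Step 5. Sensitivity to the assumptions**
- Month 3 covariate. The redacted list may include Month 3 MMVS; Protocol 4.7 Table 1 schedules visits at "3M(±1w), 6M(±1w) and 9M (±2w) after last treatment" with a blinded MMVS rating, and Table 2 has one at 3 months for controls. With an assumed Month 3 score (equal to Month 6 in 80%), the unrounded bias was −2.7 and −3.7 at 10/10, and −5.6 and −7.7 at 20/20.
- Other grade mixes (73%/10% and 90%/17% true response). Across all three mixes the unrounded bias ran from −2.7 to −4.7 at 10/10 and from −5.3 to −9.6 at 20/20. Rounded and joint gave −2.5 at 20/20 in the 73%/10% mix.
- A different data model (correlated latent improvement, 15% missing, true treated response 75%, correlation 0.9) gave imputed treated response of 37% unrounded joint, 24% unrounded separate, 71% rounded joint and 63% rounded separate.
- Complete-data analysis stayed within 0.1 point in the main-mix scenarios. This is expected when data are missing at random within arm.
- The largest Fisher p-value in any single unrounded imputed dataset was 0.005.

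**The case against.** The strongest reply is that the SAP never says unrounded values are cut at 1.0. It defines MMVS as whole grades, and a programmer may well round. The larger figures above belong to a reading that the plan does not choose, and with rounding little bias is left. That stands: what is shown is an unspecified step.

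Redaction is the second reply. The covariate list, most of SAP 3.3.3, part of SAP Section 5 and text after the Table A 18 notes are blacked out, and a conversion rule could sit there. The MCMC step is multivariate, though the visible text does not say that both sides enter one model. That also stands, so the point is limited to the visible text.

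Third, a reader might infer that rounding without joint imputation is inadequate in general. The figures do not support that: at equal missingness in the main mix it leaves 1 point or less. It does so through offsetting errors, and it reaches about +1.5 to +1.9 only when controls are missing far more often. Nothing in the documents suggests such an imbalance, and Protocol 4.1 offers controls treatment at the Month 6 visit, which is a reason to attend.

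Fourth, the per-protocol analysis is a second check on BOCF, and under the simulated missingness it would show the attenuation. It also drops subjects for other deviations (SAP 3.2.2), so it does not replace an imputation analysis on the full FAS.

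**Conclusion.** The point holds as a minor one. SAP 3.3.2 models a whole-grade score by linear regression and then applies a both-sides responder cut, with no visible rule for conversion or for linking the sides. If the values are left unrounded, and if true response is 88% / 17% with equal missingness, the analysis understates the difference by about 3 to 4 points at 10% missing and 5 to 8 points at 20%. It would then be a poor check on BOCF. With rounding, the bias in that mix is about 2 points or less in every scenario run.

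A reader might go further and infer that the plan prescribes a biased analysis, that the rule is proven absent, or that the efficacy conclusion is in doubt. The documents support none of these. The unrounded cut is only one reading, the adjacent text is redacted, and the assumed true difference of about 71 points (88 − 17) dwarfs the bias. The primary BOCF analysis does not use the imputed data, and its significance is not at risk. All sizes rest on assumed missing rates and grade mixes.

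**What to change.** In SAP 3.3.2 and the note to Table A 18, replace linear regression with logistic imputation of both-sides Month 6 responder status, given treatment and earlier MMVS. Table A 18 reports only the combined responder, so nothing more is needed, and the bias in the main-mix runs was 0.5 point or less.

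If linear regression is kept, state that the right and left scores are imputed in one model, rounded to whole grades and limited to 1–4 before responder status is derived. If a redacted passage already says this, repeat it in the Table A 18 note.

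The cost is SAP wording and minor programming. No new data are needed, and the primary analysis does not change.

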3.3.3 Primary analysis

The responder rate will be calculated for each group at Month 6 based on the blinded evaluator's assessment. CCI [REDACTED]

CCI [REDACTED]

In addition, to evaluate the impact of missing data, the primary analysis will be re-run using the PP analysis set.

Site effects will be explored by using descriptive statistics of the treatment effects by site (estimates and confidence intervals of the response rates within site).

Effective

Effective date: 2017-04-21 09:20

Version: 1.0

 GALDERMA	<small>Title</small> Statistical Analysis Plan 43CH1507	<small>Doc id</small> MA-32268

CCI
		

3.4 Safety analysis

All safety variables will be summarized descriptively based on the safety population.

 GALDERMA	<small>Title</small> Statistical Analysis Plan 43CH1507	<small>Doc id</small> MA-32268
--	---	--

Effective date: 2017-04-21 09:20

Effective

Version: 1.0

3.4.1 Extent of exposure

Data on extent of exposure and treatment procedure will be summarized by group, for initial treatment and touch-up separately. Injection volume will also be summarized for initial treatment and touch-up totally.

3.4.2 Adverse events

All AEs will be coded according to MedDRA. All AE summaries defined below will be presented by treatment (no treatment at baseline vs. all treated subjects (at baseline and Month 6)).

The number of subjects with AEs related to study product or injection procedure as well as the number of events will be summarized by SOC and preferred term (PT). In addition, AEs related to study product or injection procedure will be summarized by SOC, PT and intensity. The number of days to onset and the duration of related AEs will be summarized by SOC and PT using mean, SD, min, max and median.

Serious AEs and device deficiencies will be listed, if applicable.

Non related AEs will be summarized by SOC, PT, and intensity.

CCI

[figure not shown]

